## Inclusion of Women and Minorities

Men and women of all ethnic backgrounds will be recruited to participate. It is anticipated that the subject demographic profile will closely mirror the larger population from which they are recruited. In the previous cocaine clinical trials at our center, the percentage of females and males is approximately 30% and 70% respectively. We will continue recruitment efforts to achieve a 50 50 balance and thus permit meaningful analyses by sex across groups.

In the ongoing clinical trial, efforts are made to have the outreach coordinator present educational material and referral information at women's clinics in Houston and the surrounding communities. Advertising in papers especially directed to women, such as SingleFile (a publication with 53% female readership), and the Health and Beauty section of the Greensheet has helped in the past to enhance recruitment of women with cocaine dependence.

The ethnic representation has been 55% African-American, 44% Caucasian, 15% Hispanic, and <1% Asian. In the absence of data on the prevalence of cocaine dependence disorder in the Houston area, we cannot define ethnic base rates. The medical center environment is not known to be uniquely avoided by any particular ethnic group and patients view it as favorable and neutral. Nevertheless, we are prepared to implement recruitment procedures to ensure a more diverse patient population: These procedures include: 1) Targeted advertising in newspapers which serve minority communities (e.g., Chance, a Hispanic publication). 2) Distribution of flyers and notices in neighborhoods known to have a high minority population. 3) Engaging in outreach activities on an ongoing basis, e.g., contacting church and community leaders in the Hispanic communities to provide educational material about cocaine dependence and its consequences; providing contact information to aid referrals to clinic at the CNRA.

### **Inclusion of Children**

Children between the age of 18 and 21 years will be included in this study. This age range was chosen as the vast majority of subjects who meet criteria for cocaine dependence are over 18 years of age. In addition, brain function in children under 18 is significantly different from that of adults. The inclusion of younger subjects than this age level will increase variance in brain function.

## Data analysis plan

Initial analyses will evaluate group differences on demographic and baseline variables, will use contingency tables with chi-square testing, ANOVA's, and examination of correlations between baseline variables and snDCM results. The Friston et al. network discovery technique, Bayesian model selection (BMS), and Bayesian family level inference (BFLI) will be used to select the optimal model based on the exceedance probability of the DCM (or family of DCMs) in which DLPFC causally affects ventral striatum vs. exceedance probability of the DCM (or a family of DCMs) in which the ventral striatum causally affects the DLPFC. The parameter estimates for the endogenous DLPFC-striatal connectivity will be compared between groups using Bayesian model averaging (BMA) and also compared using analysis of covariance.

Urn randomization, a form of stratified randomization, will help ensure comparability of treatment groups on baseline severity and duration of cocaine abuse. Pretreatment task behavioral performance or demographic variables on which group differences are detected, and which are correlated with outcomes, meet the definition of confounders. In such cases, analyses will evaluate the robustness of findings after statistically controlling for the confounder. If conclusions remain unchanged after covarying for the confounder, the more parsimonious model will be reported along with a statement indicating its robustness to covariation for potential confounding. If inclusion of the covariate alters the conclusions of the analysis, both models will be reported. Treatment success is a function of two elements: (a) retention and (b) demonstrating cocaine-free status using the SRPHK1 criteria. The Treatment Effectiveness Score (TES) provides a metric for this composite outcome. TES is the sum of all cocaine-negative tests (according to SRPHK1 rules). Higher TES indicates that participants both continue to participate in the study and are negative for cocaine. For each group, BMA is conducted across all DCMs in the model space. Group difference in the gating effect by the dorsal striatum is assessed using Bayesian confidence probability. In addition, BMA is conducted across all DCMs in the model space for each subject in the medication group and in the placebo group. Evaluation of differential treatment response, measured by the TES, as a function of the averaged (across the DCM model space) gating effect, will use Poisson regression. Violations of assumptions of dispersion will result in the use of more appropriate approaches such as zero-inflated Poisson, negative binomial, or zero-inflated negative binomial models. Regression of treatment, averaged gating, and their interaction will permit evaluation of differential treatment response as function of gating. The critical element in doing so is the evaluation of the interaction term. Given that the current study is powered to detect group differences, it is likely underpowered to detect an interaction. Brookes, et al. demonstrate that for studies with 80% power to detect a between-groups effect, power to detect an interaction effect of the same magnitude as the main effect is approximately 29%. One solution is to adopt a Bayesian subgroup analysis approach. This approach utilizes the posterior distribution of the interaction parameter to estimate the probability that it exceeds some number (e.g., for Poisson regression a Risk Ratio of 1.0). Specification of vague neutral priors will reflect uncertainty regarding parameter values, utilizing prior distributions for the lower order effects that are neutral and diffuse with specification  $\sim N(0, 1 \times 10^{-6})$  on the log scale (i.e., centered at the null hypothesis with a 95% Credible Interval of  $\pm 1960$ ) for all coefficients, and  $\sim U(0, 100)$  for any required dispersion terms. Examination of the interaction of treatment and the subgroup index forms the crux of the evaluation of the subgroup effect. For evaluating the interaction representing the differential subgroup effect, analysis will be conducted in two ways: (a) utilizing diffuse, indifferent priors ( $\sim N(0, 1 \times 10^{-6})$ ) on the log scale for the interaction coefficients, and (b) using informative skeptical priors for the coefficients will evaluate sensitivity of statistical conclusions to specification of priors. Informative, skeptical priors will be derived via the method first proposed by Dixon and Simon. Evaluation of resulting posterior distributions will permit conclusions regarding the probability that subgroup/interaction effects of varying magnitudes obtain. Examples of this use of the posterior distribution may be found in Green et al. (2009). Bayesian modeling will use SAS v9.2 (Proc Genmod and Proc Monte-Carlo Markov chain [MCMC]), and in WinBugs 1.4.3 (<http://www.mrc-bsu.cam.ac.uk/bugs>). Convergence of Bayesian analyses on the posterior distributions via MCMC will be assessed via graphical (Trace Plot, Autocorrelation Plot) and quantitative (Geweke Diagnostics, Gelman-Rubin Diagnostics, and Heidelberger-Welsh Diagnostics) evidence. Evaluation of posterior distributions will permit statements regarding the probability that effects of varying magnitudes exist, given the data.

While the use of urn randomization will likely result in comparable groups, substantial heterogeneity may still exist within conditions on baseline variables such as severity, duration of use, and impulsivity. We propose subgroup analyses following the procedures described above. This will determine the degree to which baseline variables moderate the interaction of treatment and snDCM.

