unpublished pilot data (Section C.2.4) have shown that the baseline fMRI working memory activation and the effective connectivity elicited by the working memory task are predictive of treatment outcome with DA enhancing medications in COs. Previous studies have shown that cocaine use can induce impaired response inhibition in both human ([1-8] and see [9] for review) and animals ([10-12] and see [13] for review). In addition, there is evidence ([15-19] and see [20, 21] for review) supporting the hypothesis that DA modulates response inhibition. Furthermore, impulsive personality traits predict DA-dependent changes in frontostriatal activity during component processes of working memory [117]. A study [100] conducted by our group has shown that trait impulsivity is predictive of cocaine addiction treatment outcome. *The relationship between cognitive domains and DA is relevant because the major objective of this study is to predict treatment outcome of DA enhancing medications.*

**Summary of Significance:** (a) Establishing the directional relationship between PFC and striatum and the role of striatal gating in cocaine treatment response will significantly improve our understanding of dopaminergic and pharmacotherapeutic mechanisms in COs. (b) The pilot data (Section C.2.4) suggest that treatment outcome in COs with low pretreatment striatal OA can be improved with OA enhancing treatments by increasing striatal OA function, which we theorize increases striatal gating of cortico-cortico connections. Thus the evidence supporting the hypothesized striatal gating mechanism will have significant implication in cocaine addiction treatment. (c) An issue in cocaine dependence research is the lack of clinically useful biomarkers for pharmacotherapies. Effective connectivity as measured by snOCM may ultimately lead to clinically useful biomarkers for cocaine dependence and its treatment.

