**C. Approach:**

**C.1 Overview of Study Design.** *The objective of this study is to use baseline (pretreatment) snDCM to predict the treatment response to DA medication.*

**C.2 Preliminary Studies:** C.2.1. An analysis of regional fMRI activations showed that pretreatment thalamic activation predicted treatment response in COs [35]. This study examined the relationship between pretreatment working-memory elicited regional activations and subsequent treatment response in treatment-seeking early abstinence COs. Nineteen COs who were randomized to treatment studies and 14 non-drug using controls underwent fMRI while performing a working memory task with variable memory load, as parameterized by two levels of memory delay and three levels of digit load (number of digits presented in each visual stimulus). Group comparison showed that COs had significantly lower regional activation in caudate, putamen, cingulate gyrus, middle and superior frontal gyri, inferior frontal gyrus pars triangularis and pars opercularis, medial orbitofrontal cortex, precentral gyrus, and thalamus compared to non-drug using controls. These brain regions are known to be part of a circuit associated with reward, conditioning/memory, executive control, and motivation/drive [92]. Within COs, pretreatment thalamic activation significantly correlated with the subsequent treatment response. Subjects with pretreatment thalamic deactivation showed the poorest treatment response, possibly related to thalamic involvement in mesocortical and mesolimbic OA projections. *This study supports our research group's capacity to carry out fMRI studies in COs and our research group's expertise in treatment response prediction research.*

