decreased DA caused by decreased prefrontal-striatal glutamatergic neurotransmission [44, 85, 86, 92]. Nonparametric Spearman correlation analysis showed that the pretreatment gating effect by the dorsal striatum on the connection from IFC to PPC was inversely related to the Treatment Effectiveness score (TES), a measure of relative abstinence from cocaine use, after 8 weeks of treatment with OA enhancing medications ( $r = -0.69$ ,  $p=0.12$ , see figure in this section). These preliminary findings are consistent with the theory that OA enhancement may be a useful target for pharmacotherapy of cocaine dependence in COs who have pretreatment hypodopaminergic state [81, 88, 89]. A recent study by Martinez et al. [87] showed that low pretreatment striatal OA transmission in COs was associated with treatment failure from behavioral therapy alone (without any pharmacological treatment). One may speculate that COs with low pretreatment OA in that study would benefit from the addition of OA enhancing medication [44]. The results of [87] and our preliminary findings are consistent with the theory that preexisting differences between COs in OA circuits may be a mechanism underlying variability in responsiveness to different treatments [44]. *This pilot study supports our expertise in the use of snDCM and Hypotheses 1 and 2.*

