C.2.5 Our pilot fMRI study testing response inhibition in COs showed: (a) activation in an orbitofrontal-striatal-thalamica/circuit; and (b) positive correlation of caudate activation with performance, and negative correlation of caudate activation with severity of cocaine addiction. Eleven COs (cocaine group) and ten age-matched controls (control group) were included in an event-related fMRI study of response inhibition. The fMRI data were acquired while the subjects performed a Go/NoGo task [1], in which there are two levels of difficulty in NoGo trials (Easy NoGo and Hard NoGo trials), (see section C.4.6 and reference [1] for description). An SPM univariate 2nd level analysis of the fMRI data across both groups revealed that the main effects of correct NoGo trials relative to Go trials showed activation in four clusters (uncorrected 2-tail cluster  $P < 0.05$ , cluster size  $> 238$  voxels) that were found in portions of LR thalamus, L posterior cingulate, LR supplemental motor area, L superior frontal gyrus (g), R superior parietal g, R angular g, R inferior parietal lobule, L fusiform g, and L parahippocampal g. There was no significant interaction of activation with task difficulty. Within COs, whole brain voxel-wise SPM regression analysis showed positive correlation of NoGo activation with NoGo accuracy ( $d'$ ) in portions of L caudate, R middle cingulate, R inferior parietal lobule, R medial orbital g, R putamen, R pallidum, R rectus g, and R lateral orbitofrontal cortex (cluster 2-tail false discovery rate [FOR] corrected  $P < 0.10$ , cluster size  $> 465$  voxels). Whole brain voxel-wise SPM regression analysis also showed negative correlation of NoGo activation with severity of cocaine addiction (total KMSK score [151]) in portions of L caudate, L fusiform g, L angular g, L insula, L olfactory g, L medial orbital g, L rectus g, L putamen, L parahippocampal g, L middle temporal g, and L inferior temporal g (cluster 2-tail FOR corrected  $P < 0.10$ , cluster size  $> 443$  voxels). *This pilot study supports our expertise in the use of a Go/NoGo fMRI task in studying response inhibition in COs, and the results support the regions of interest selected for snDCM analysis to test Hypothesis 3 (C.4.19.2).*

C.3 Description of the Clinical Trial. The objective of this proposal is to use pretreatment snOCM to predict the treatment response to OA enhancing medication in COs.

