C.3.1 Participants and Recruitment for the Clinical Trial: Male and female treatment-seeking individuals, 18 to 55 years old, who meet current OSM-IV criteria for cocaine dependence and report using cocaine within the past 30 days are enrolled. Eligible subjects are required to submit at least one positive urine toxicology screen for the cocaine metabolite benzoylecgonine (BE)  $> 300$  ng/ml, during the one-week screening and pretreatment assessment period. Subjects currently dependent on any psychoactive substance other than cocaine, nicotine, or marijuana are excluded. 60 treatment-seeking COs will be recruited.

C.3.2 Screening, Pretreatment, Randomization for the Clinical Trial: Candidates signing written informed consent enter a one-weiintake and assessment phase to evaluate eligibility and administer baseline pretreatment measures. Those who fail to return for required visits during this period are not randomized to treatment so as to reduce early treatment dropout rates [152]. An *urn randomization [153] procedure assigns subjects to one of the four treatment groups.* This procedure balances groups on pretreatment characteristics that may influence measures of cognitive performance and/or treatment outcome. The variables include (a) severity of cocaine use, based on days using cocaine in past 30 days and KMSK score [151]; (b) lifetime duration of cocaine use; (c) level of marijuana use, based on days using in past 30 days; (d) Barratt Impulsiveness Scale (BIS) [202], measuring trait impulsivity.

*In the Clinical Trial, there is one active medication arm and one placebo arm.* Equal allocation to treatment conditions is expected, as follows: 30 COs assigned levodopa/carbidopa 400/100 BID, and 30 COs

assigned placebo. Treatment assignment is concealed to all staff, including the investigators. Only the study pharmacist who dispenses the study medications is unblinded to participants' assigned condition. At each clinic visit (Monday, Wednesday, Friday) subjects are administered the medication at the dispensing window and given take-home doses for intervening days.

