Urn randomization [153], a form of stratified randomization, will help ensure comparability of treatment groups on baseline severity and duration of cocaine abuse. Pretreatment task behavioral performance or demographic variables on which group differences are detected, and which are correlated with outcomes, meet the definition of confounders [192, 193]. In such cases, analyses will evaluate the robustness of findings after statistically controlling for the confounder. If conclusions remain unchanged after covarying for the confounder, the more parsimonious model will be reported along with a statement indicating its robustness to covariation for potential confounding. If inclusion of the covariate alters the conclusions of the analysis, both models will be reported. Treatment success is a function of two elements: (a) retention and (b) demonstrating cocaine-free status using the SRPHK1 criteria (see section C.3.4). The Treatment Effectiveness Score (TES) provides a metric for this composite outcome [194]. TES is the sum of all cocaine-negative tests (according to SRPHK1 rules). Higher TES indicates that participants both continue to participate in the study and are negative for cocaine. For each group, BMA (section C.4.19.4) is conducted across all OCMs in the model space. Group difference in the gating effect by the dorsal striatum is assessed using Bayesian confidence probability [195]. In addition, BMA is conducted across all OCMs in the model space for each subject in the medication group and in the placebo group. Evaluation of differential treatment response, measured by the TES, as a function of the averaged (across the OCM model space) gating effect, will use Poisson regression. Violations of assumptions of dispersion will result in the use of more appropriate approaches such as zero-inflated Poisson, negative binomial, or zero-inflated negative binomial models. Regression of treatment, averaged gating, and their interaction will permit evaluation of differential treatment response as function of gating. The critical element in doing so is the evaluation of the interaction term. Given that the current study is powered to detect group differences, it is likely underpowered to detect an interaction. Brookes, et al. [196] demonstrate that for studies with 80% power to detect a between-groups effect, power to detect an interaction effect of the same magnitude as the main effect is approximately 29%. One solution is to adopt a Bayesian subgroup analysis approach [197-201]. This approach utilizes the posterior distribution of the interaction parameter to estimate the

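### The confounder rule for the TES models tests for group differences, so it cannot reveal confounding of the gating effect, and severity and impulsivity are not eligible under it

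*SAP*

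**What the plan says.** The TES model is the same in Protocol C.4.20 and the SAP data analysis plan: "Regression of treatment, averaged gating, and their interaction will permit evaluation of differential treatment response as function of gating". It has no baseline covariate. The only route to one is the rule "Pretreatment task behavioral performance or demographic variables on which group differences are detected, and which are correlated with outcomes, meet the definition of confounders". A variable that qualifies leads to a robustness check, and the model without it is reported if the conclusion does not change.

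Other parts of the documents bear on this:

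- **Urn factors (C.3.2).** Severity, duration of use, marijuana use and BIS are balanced. Of the urn procedure the protocol says: "This procedure balances groups on pretreatment characteristics that may influence measures of cognitive performance and/or treatment outcome".
- **Impulsivity (A.6).** The protocol states that "trait impulsivity is predictive of cocaine addiction treatment outcome" and that "impulsive personality traits predict DA-dependent changes in frontostriatal activity during component processes of working memory". Working memory is the Aim 2 domain.
- **Severity (C.2.5).** The Go/NoGo pilot reports "positive correlation of caudate activation with performance, and negative correlation of caudate activation with severity of cocaine addiction". Response inhibition is the Aim 3 domain, and Aim 3 reuses the Aim 1 and 2 analysis.
- **Baseline correlations with snDCM results.** These are examined in the initial analyses, but no action follows from them.
- **Subgroup analyses.** Severity, duration and impulsivity appear as moderators of the treatment-by-snDCM interaction.
- **Task performance.** C.4.7 says pretreatment performance will be a covariate. C.4.20 and the SAP make that conditional.

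**The concern.** Randomisation balances the arms. It does not balance patients with low gating against patients with high gating. If more severe users tend to have a different gating value and also a different TES, the gating slope carries part of the severity effect. A comparison of severity between arms cannot show this.

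The rule therefore fails in two ways within the randomised arms. It looks at the wrong association, and it restricts candidates to task performance and demographics, which excludes severity and BIS. The rule does not define which groups it means, but no reading of it tests association with gating.

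At stake is what a gating-TES slope may be said to show. The protocol reads gating as an indicator of dopamine function and wants to study the mechanism of response (A.5, C.4.20). An unadjusted slope cannot separate that reading from severity or impulsivity measured by interview and questionnaire.

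**Working it through.** **Inputs from the documents:** 24 analysed per arm, so 48 patients in the TES model (C.4.1); effect size 0.60, two-sided 5%, n = 24, stated power 86% (C.4.21); a Spearman correlation in the pilot (C.2.4).

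**Assumed, because the documents give none:** the gating-severity correlation, the severity slope, and any severity-by-treatment effect. A two-sided 5% test stands in for the Bayesian analysis, for which no posterior threshold is stated.

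**1. The plan's own figure.** Fisher z with the Spearman variance 1.06/(n - 3): atanh(0.60) = 0.693; 0.693 × sqrt(21/1.06) = 3.085; Φ(3.085 - 1.960) = 87%. Direct simulation of the Spearman test gives 85%. The stated 86% reproduces, as the power of an unadjusted correlation.

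**2. What the screen detects.** Between randomised arms, a 5% test flags a baseline variable 5% of the time whatever its link to gating. Take an eligible variable correlated 0.3, 0.4 or 0.5 with both gating and TES. The full rule (arm difference plus correlation with outcome) flags it in 2.9%, 4.2% or 4.6% of simulated trials. Urn balancing would lower this for urn factors.

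**3. Bias in the gating slope.** With standardised gating and severity, correlation ρ and residual SD 1, the expected unadjusted slope is β(gating) + β(severity) × ρ. Take β(gating) = 0 and β(severity) = -0.6:

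- ρ = -0.3: bias = +0.18; SE ≈ sqrt((1 + 0.36 × 0.91)/44) = 0.174; ratio 1.04.
- ρ = -0.5: bias = +0.30; SE ≈ sqrt((1 + 0.36 × 0.75)/44) = 0.170; ratio 1.77.

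False gating effects by simulation, negative (the hypothesised direction) / positive:

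| ρ | Linear, unadjusted | Count model, unadjusted |
|---|---|---|
| -0.3 | 0.1 / 17.7% | 0.1 / 15.5% |
| -0.5 | 0.0 / 40.7% | 0.1 / 35.4% |
| +0.3 | 17.0 / 0.1% | 15.9 / 0.1% |
| +0.5 | 40.6 / 0.0% | 36.9 / 0.0% |

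With severity in the model, each side is about 2.5%. Separate linear runs at ρ = -0.3 and -0.5 agree (18% and 41 to 42% in total). The count model treats TES as negatives out of 36 visits (3 × 12) with overdispersion.

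**4. The same point at the plan's effect size.** Partial correlation = (rGY - rGS × rSY)/sqrt((1 - rGS²)(1 - rSY²)). With rGY = -0.60 and rSY = -0.3:

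- rGS = +0.3: (-0.60 + 0.09)/0.91 = -0.56.
- rGS = -0.3: (-0.60 - 0.09)/0.91 = -0.76.

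Adjustment can weaken or strengthen the association.

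**5. The interaction.** No true gating effect, linear model, ρ = -0.3 / -0.5:

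- Equal severity slopes in both arms: false positives about 5%.
- Slopes -0.4 on medication and -0.8 on placebo: 6% / 9%.
- Slopes -0.2 and -1.0, which is extreme: 10% / 20%.

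In the last case at ρ = -0.5, a severity main effect alone leaves about 23%. Adding severity × treatment restores 5%.

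**The case against.** **Prediction is the stated aim.** The protocol's objective is to "use baseline (pretreatment) snDCM to predict the treatment response to DA medication", and a confounded marker can still predict. This stands. The three-term slope is the right answer to that question and should stay. It does not cover the dopamine reading, nor any claim that a 90-minute scan adds to simple baseline measures.

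**The plan already uses these variables.** This stands in part. If the moderator models are hierarchical, they would contain severity × treatment. But neither they nor the baseline correlations with snDCM results are tied to the main TES conclusion.

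**Adjustment may remove real signal.** A.5 presents low dopamine as a driver of drug taking and of the transition to dependence, so severity may lie partly downstream of what gating reflects. This stands as a caveat on the adjusted model.

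**The rule is sound elsewhere.** It is reasonable for the non-randomised comparison of patients with controls in Aim 1. This stands, so the change is limited to the TES models.

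**The direction might be inferred from the pilot.** A reader might take the negative severity-caudate correlation to mean that omitting severity would mask the hypothesised inverse slope, or might fear that the omission would create it. The documents support neither. The pilot result is regional activation in 11 patients on the Go/NoGo task at a corrected P < 0.10. It is not gating. For BIS no sign is given at all.

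**Conclusion.** The rule cannot do its job for gating within the randomised arms, and the two variables with the best documented claim to matter are outside it. That follows from the text and needs no assumption. The gating-TES slope may be biased in either direction. How much, and which way, cannot be known from the documents. The 18% and 41 to 42% are illustrations that rest on an assumed severity slope and assumed correlations.

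Two stronger readings should be resisted. One is that the power statement is wrong: 86% is for an unadjusted correlation and reproduces as such. The other is that the interaction, which the plan calls critical, is generally biased. It is biased only if severity or BIS also modifies the treatment effect, which no document reports. With equal severity slopes its error rate stays at about 5%.

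**What to change.** For the TES models, drop the group-difference trigger and always report two prespecified models:

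1. Treatment, gating and gating × treatment, labelled as the answer to the prediction objective.
2. The same plus BIS total and one severity measure, named in the SAP now, before any gating or TES data are seen. Label it as the test of whether gating carries information beyond severity and impulsivity. Any claim that gating reflects a dopamine mechanism, or adds to simple baseline measures, must hold here, with the caveat that severity may be partly downstream of low dopamine.

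As a labelled sensitivity analysis for the interaction, add severity × treatment and BIS × treatment to model 2.

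Reconcile C.4.7 with C.4.20 and the SAP by making pretreatment performance a further labelled sensitivity covariate. C.4.19.1 ties working-memory capacity to the gated IFC-PPC connection, so forcing performance in may over-adjust. Report any disagreement between models.

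**Cost.** The change is SAP wording; C.3.2 already uses severity and BIS for the urn.

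- *Interaction power, model 2.* Two of 44 residual degrees of freedom are used. The plan's cited 29% corresponds to noncentrality 1.437. Dividing by sqrt((1 - R²) × 43/41) gives 28, 30, 34 and 37% if the covariates explain 0, 10, 20 and 30% of TES variance and are unrelated to gating.
- *Interaction power, sensitivity model.* Four degrees of freedom are used, so the factor is 43/39. Over the same R² range, power is about 23 to 30% if severity and BIS each correlate 0.3 with gating (noncentrality × sqrt(1 - 0.18)), and 16 to 20% at 0.5 each (× sqrt(1 - 0.50)).
- *Precision of the slope.* Covariates tied to gating but not to TES cost precision. Assume a gating slope of -0.4 common to both arms (the plan does not claim a common slope), a severity slope of -0.3 and a correlation of -0.3. Linear-model power is then 48% unadjusted and 67 to 68% with severity. If BIS is added but has no effect on TES, it is 63% or 56% when BIS correlates 0.3 or 0.5 with gating. Forcing in performance as well, likewise without effect, gives 55 to 59% or 35 to 46%, a further reason to keep it out of model 2.
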